**Vulnerable Populations:**

The research does not involve individuals who are vulnerable to coercion or undue influence.

**Sharing of Results with Subjects:**

Subjects will be provided a copy of their DXA, BIA, and 3D optical scans that can be shared, if wanted, with their health care provider.

**Setting:**

The study will be carried out at PBRC and MGH. Certified radiological technicians at both clinical sites will conduct the DXA scans.

**Personnel Responsible for the Safety Review and its Frequency:**

The co-principal investigators (Drs. [name] and [name]) will be responsible for monitoring the data, assuring protocol compliance, and conducting the safety reviews at the specified frequency of once per month. During the review process, Drs. [name] and [name] will evaluate whether the study should continue unchanged, require modification/ amendment, or close to enrollment.

The PI's and the Institutional Review Board (IRB) have the authority to stop or suspend the study or require modifications.

This protocol presents minimal risks to the subjects, and adverse events or other problems are not anticipated. In the unlikely event that such events occur, Drs. [name] and [name] are responsible for reporting serious, unanticipated and related adverse events or unanticipated problems involving risks to subjects or others to the IRB. Drs. [name] and [name] will apprise fellow investigators and study personnel of all adverse events that occur during the conduct of this research project through regular study meetings and via email.

**Employee participation:**

PBRC or MGH employees who participate in this research protocol will do so voluntarily, and of their own free will. None of those enrolled in this project will report to any of the study investigators, including the Principal Investigators.

**Timeframe:**

The study will be completed over two months

**Statistical Design and Analysis:**

Drs. [name] and [name] will analyze the data using JMP, Excel, and other conventional software. Regression analysis will be used to test the main study hypothesis with %fat measured by the VBC device and by DXA as the reference method. Similar comparisons will be made for the other test systems (e.g., BIA). A secondary series of analyses will be conducted using BodPod as the reference method. Bland-Altman plots will be used to detect between-method bias. Coefficient of variations will be calculated using the duplicate measurements acquired by the VBC and other test systems.

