## **Hypothesis:**

We hypothesize that the VBC device will be equal to or more accurate than clinical grade (DXA, Bod Pod) and BIA systems for measuring body composition.

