## **Aims:**

The study hypothesis will be tested as follows. Each subject will complete VBC, DXA, anthropometric, BodPod, and BIA analysis at either PBRC or MGH. The acquired data will then be used to accomplish the specific aims:

1. Identify the associations of body composition acquired by the VBC with those estimated by DXA, BodPod, and BIA.

2. Describe the precision and accuracy of the VBC-derived scans.

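### DXA is both a comparator and the reference in the main analysis, and no contrast of device errors or margin is set to decide whether VBC is as accurate as the other systems

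*Combined protocol and SAP*

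**What the plan says.** - **Hypothesis:** VBC will be "equal to or more accurate than clinical grade (DXA, Bod Pod) and BIA systems" for measuring body composition. DXA is one of the named comparators.
- **Aims:** the section opens with "The study hypothesis will be tested as follows". The two aims that follow are to "Identify the associations of body composition acquired by the VBC with those estimated by DXA, BodPod, and BIA" and to describe VBC's precision and accuracy.
- **Statistical Design and Analysis:** "Regression analysis will be used to test the main study hypothesis" "with %fat measured by the VBC device and by DXA as the reference method". The other systems, with BIA as the example, get a like analysis. Then: "A secondary series of analyses will be conducted using BodPod as the reference method" and "Bland-Altman plots will be used to detect between-method bias". Coefficients of variation come from the duplicate readings.
- **Study Endpoints:** only recruitment of the stratified sample is named.
- **Subjects and Design:** VBC and BIA are measured twice per participant, BodPod and DXA once.

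The document states no accuracy statistic, no margin, no acceptable limits of agreement and no significance level.

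**The concern.** The hypothesis is comparative, and two sections promise to test it. A comparative accuracy claim needs a reference that is not itself one of the devices being ranked, a measure of error, a contrast of that error between devices and, for a claim of equality, a margin. The analysis section supplies a reference, but it is one of the comparators. It does not supply the other three.

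Two things are at stake. The DXA part of the hypothesis cannot be confirmed in the analysis named to test it. For Bod Pod and BIA, the verdict could depend on which of several outputs is emphasised once the data are in.

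**Working it through.** The plan gives no figure to reproduce: 132 participants is stated without a power or precision calculation. All SDs and biases below are assumptions, in %fat points.

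**1. DXA as comparator and reference.** Error against DXA is (device − DXA). For DXA this is 0 in every participant, however good or poor DXA is. Assume independent, unbiased true errors with SD 1 for VBC, 2 for DXA and 2 for BodPod, so that VBC is truly better than DXA.
- Root mean square error against DXA: VBC √(1² + 2²) = 2.24; DXA 0.
- Against BodPod: VBC √(1² + 2²) = 2.24; DXA √(2² + 2²) = 2.83.

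The main analysis puts the two devices in the wrong order and the BodPod series puts them in the right order. The latter depends on independence. If DXA and BodPod errors have correlation ρ and VBC's are uncorrelated with BodPod's, DXA's mean square error against BodPod is 4 + 4 − 8ρ. This falls below VBC's 5 once ρ exceeds 3/8, and the order reverses. BodPod's own error is zero in this series, so it cannot be ranked there.

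**2. What each planned output measures.**
- R² and the standard error of estimate (SEE): scatter about a fitted line. A constant bias is absorbed by the intercept.
- Bland-Altman plots: bias and spread within one device-reference pair.
- Coefficients of variation: repeatability, not accuracy.

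None is a contrast of VBC's error with another device's.

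**3. Can the outputs disagree?** Assume n = 132, DXA %fat SD 9, and errors independent of the DXA value. VBC has bias +2 and error SD 3.5; the comparator has bias 0 and SD 4.2.

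| Output | Formula | VBC | Comparator | Favours |
|---|---|---|---|---|
| Bias (95% CI) | bias ± 1.96·SD/√132 | 2.0 (1.4 to 2.6) | 0.0 (−0.7 to 0.7) | comparator |
| Limits-of-agreement width | 2·1.96·SD | 13.7 | 16.5 | VBC |
| R² | 81/(81 + SD²) | 0.87 | 0.82 | VBC |
| SEE | 9·√(1 − R²) | 3.3 | 3.8 | VBC |
| Mean absolute error | folded normal | 3.24 | 3.35 | nearly tied |

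The folded-normal mean is SD·√(2/π)·exp(−bias²/(2·SD²)) + bias·(1 − 2Φ(−bias/SD)). For VBC this is 2.37 + 0.86 = 3.24 before rounding of the terms; for the comparator it is 4.2 × 0.798 = 3.35.

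**4. What a paired contrast would return in the same example.** The variance of an absolute error is bias² + SD² − (mean absolute error)²: 16.25 − 10.47 = 5.78 for VBC and 17.64 − 11.23 = 6.41 for the comparator. If the two are independent, the difference has SD √12.19 = 3.49 and a 95% half-width of 1.96 × 3.49/√132 = 0.60. The result is one number, −0.11 (−0.71 to 0.49), to be judged against a margin.

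**5. Limit of that contrast.** Error in the single DXA scan adds to both devices' apparent error. For unbiased devices with SD 4 and 3 and independent errors, the difference in mean absolute error is √(2/π)·[√(16 + d²) − √(9 + d²)], where d is the DXA error SD. It is 0.80 at d = 0, 0.69 at d = 2 and 0.60 at d = 3. True differences shrink towards zero, which makes equality easier to conclude.

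**The case against.** The strongest reply is that this is a one-visit, cross-sectional study of a wellness device with descriptive aims, which the analysis section delivers. On that view the hypothesis is only a working statement. All systems are measured in the same people against one reference, so readers can compare them, and regression could be used to check that the slope is 1 and the intercept 0.

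Much of this stands. The descriptive aims are served, and the missing contrast, metric and margin are under-specification rather than contradiction. It does not dispose of the point, because the Aims and Statistical Design and Analysis sections both say that the hypothesis will be tested. Side-by-side display is not a decision rule. A slope-and-intercept check, which the plan does not mention, would still concern one device against the reference.

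A reader might go further and infer any of the following, none of which the documents support:
- **The study cannot compare VBC with DXA at all.** The BodPod-referenced series can do so, under the independence condition.
- **The outputs will probably conflict.** The example uses a chosen bias and SD, and the documents give neither.
- **The data collection is inadequate.** Paired readings on every device named in the hypothesis are already planned.

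**Conclusion.** The point holds in two parts of different weight.

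1. **Wrong as written:** DXA is a comparator in the hypothesis and the reference in the analysis meant to test it, so the DXA part cannot be confirmed in the main analysis. This follows from the definition of error and needs no numerical assumption. The BodPod series eases it only partly: it is secondary, needs independent errors, and gives BodPod the same double role.
2. **Under-specified:** for Bod Pod and BIA there is no contrast of VBC's error with the other device's, no chosen accuracy measure and no margin for equality, so no rule set in advance can confirm or refute the claim.

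The numerical example rests wholly on assumed errors. This should be fixed before analysis, but the wording and analysis can be changed without affecting data collection.

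**What to change.** Either option is sound.

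**(a) Keep the comparative claim.**
- Remove DXA as a comparator from the Hypothesis, or contrast VBC with DXA only in the BodPod-referenced series, with the independence assumption stated.
- In Statistical Design and Analysis, make the test a paired within-participant contrast of error against DXA for Bod Pod and for each BIA system, for example |VBC − DXA| minus |comparator − DXA| with a 95% CI. Other error measures are defensible.
- Fix the measure, the margin and the handling of duplicates before analysis. Duplicates matter. If single-reading error SD is 4 (assumed), averaging two VBC scans against one BodPod reading lowers VBC's mean absolute error by √(2/π)·[4 − √(16 − r²/2)]. That is 0.05 points for a repeat SD r of 1 and 0.21 for r of 2.
- For each comparator, claim that VBC is at least as accurate only if the upper limit is below the margin, and more accurate only if it is below 0.
- State that error in the single DXA scan dilutes differences, and set the margin with this in mind.
- Keep regression and Bland-Altman as supporting analyses.

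**(b) Drop the comparative claim.** Reword the Hypothesis to match the descriptive aims, and align the statements in Aims and in Statistical Design and Analysis that the hypothesis will be tested. Three sections change, not one.

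Neither option needs new measurements. Option (a) costs some drafting and an agreed margin, and exposes the hypothesis to clear failure. Option (b) gives up the comparative claim.

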## **Background:**

Optical imaging systems are rapidly evolving and are now increasingly being used in research, clinical, and home settings. The VBC 2D imaging device operates through a smart-phone and provides the user with estimates of percent body fat and other body composition estimates. The VBC is not intended for any diagnostic use, is a general-purpose wellness device based on the FDA's Mobile Medical Application and General Wellness guidance, and is thus exempt from IND requirements.

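### The accuracy hypothesis is to be tested by a regression with no stated statistic or direction, and the usual regression summaries do not measure the error of the reading the user sees

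*Combined protocol and SAP*

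**What the plan says.** The Hypothesis section makes a comparative accuracy claim: "the VBC device will be equal to or more accurate than clinical grade (DXA, Bod Pod) and BIA systems". Under Aims, association with the other methods is the first aim. The second is separate: "Describe the precision and accuracy of the VBC-derived scans".

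Statistical Design and Analysis assigns the test of the main hypothesis to regression: "Regression analysis will be used to test the main study hypothesis with %fat measured by the VBC device" "and by DXA as the reference method". The other systems, such as BIA, are to be compared similarly, and a secondary series uses BodPod as reference. The section does not say which regression output decides the hypothesis, which method is the response, or how one device is to be compared with another.

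The same section adds: "Bland-Altman plots will be used to detect between-method bias". It gives these plots no role in testing the hypothesis or comparing devices.

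Background says that the smartphone system "provides the user with estimates of percent body fat and other body composition estimates". What reaches the user is therefore the raw reading.

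**The concern.** Accuracy here means how close a displayed %fat is to the reference. A fitted regression estimates an intercept and a slope for each device from this sample, and its fit statistics describe what is left after that recalibration. The user gets no such recalibration.

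If the claim against BIA or BodPod were decided on R2 or residual error, a device that reads several points high could be declared at least as accurate as one that reads correctly. Because the deciding statistic is left open, it could also be chosen after the results are known.

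**Working it through.** **Inputs.** From the document: 132 participants (IRB Review History; Subjects and Design). It gives no SD, bias, scatter, margin, alpha or power, so there is no planned figure to reproduce, and every other input below is an assumption.

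**Model.** Device = m + c + b(DXA − m) + error, where m and σ are the mean and SD of DXA %fat, c is the offset at the mean, b the slope and s the scatter SD.

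- R2 = b²σ² / (b²σ² + s²)
- Residual error, DXA regressed on device = σ√(1 − R2)
- Residual SD, device regressed on DXA = s
- Raw RMSE = √(c² + (1 − b)²σ² + s²)

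The offset c enters only the last formula.

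**Step 1: invariance.** In one simulated sample of 132, the same readings were left as x, shifted to x + 5, and rescaled to 10 + 0.7x. All three gave R2 0.8634 and residual error of DXA on device 2.997. Raw RMSE was 3.21, 5.46 and 3.37. This is algebra and holds for any data.

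**Step 2: closed form, σ = 9.**

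| b, c, s | R2 | Residual error, DXA on device | Residual SD, device on DXA | Raw RMSE |
|---|---|---|---|---|
| 1, 0, 3 | 81/90 = 0.90 | 2.85 | 3.0 | √9 = 3.0 |
| 0.8, 3, 2.4 | 51.84/57.6 = 0.90 | 2.85 | 2.4 | √(9 + 3.24 + 5.76) = 4.2 |
| 1, 4, 3 | 81/90 = 0.90 | 2.85 | 3.0 | √(16 + 9) = 5.0 |

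The 2.85 is 9√0.10. R2 and the residual error of DXA on device cannot separate the three rows.

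**Step 3: how often the ranking reverses.** These are 4,000 simulated studies of 132 per cell, with DXA mean 33. The calibrated device has b = 1, c = 0, s = 3. Each cell is the share of studies in which the miscalibrated device has both the higher R2 and the larger raw RMSE.

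| Miscalibrated device | σ = 6 | σ = 8 | σ = 10 |
|---|---|---|---|
| Offset +5, s = 2.5 | 96.6% | 96.9% | 97.1% |
| Offset +3, s = 2.5 | 96.0% | 96.5% | 97.5% |
| Slope 0.7, no offset, s = 1.75 | 0.6% | 42.2% | 92.4% |

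Check of the first row at σ = 8: R2 is 64/70.25 = 0.911 against 64/73 = 0.877 for the calibrated device, while raw RMSE is √(25 + 6.25) = 5.59 against 3.0.

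The third row varies because the raw squared error is 0.09σ² + 3.0625. This equals the calibrated device's 9 at σ² = 5.9375/0.09 = 66.0, or σ of about 8.1. Below that spread the compressed device really does have the smaller raw error.

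**Step 4: what Bland-Altman adds.** The plots use raw differences. Their mean estimates c, and their SD estimates √((1 − b)²σ² + s²). Squaring and adding the two gives the squared raw RMSE. A trend in the differences shows a slope error: in the Step 1 sample the slope of the differences on the means was 0.06 for x and −0.30 for 10 + 0.7x.

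**The case against.** The strongest reply is that the plan names neither R2 nor residual error, and that regression also yields an intercept and a slope. Testing these against 0 and 1 is a calibration check. That is right, and a reader who inferred that regression as such ignores miscalibration would go beyond the document. What stands is that no such test is specified, and that it would reveal miscalibration in one device without ranking several.

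A reader might also infer that the plan has no check on bias. It does: the Bland-Altman plots can show a constant offset and a proportional one, as Step 4 shows. The gap is that the hypothesis is assigned to the regression, and the plots carry no stated criterion, confidence interval or comparison between devices.

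A third tempting reading is that regression actively favours a device that compresses the range. In the slope 0.8 example, the residual SD of the device regressed on DXA did favour the worse-reading device in 99% of simulated studies. That needs two things the document does not supply: this direction of regression, and scatter that shrinks with the slope (3.0 × 0.8 = 2.4). With DXA as the response, or on R2, the two devices tie at about half each. With scatter held fixed, compression leaves that residual SD unchanged.

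Finally, all the magnitudes rest on assumed inputs. This limits what can be said about how often rankings reverse, but not the invariance itself.

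**Conclusion.** The point holds in a bounded form. The accuracy hypothesis is assigned to a regression whose statistic and direction are not stated, and the usual fit summaries do not measure raw accuracy. R2 and the residual error of DXA on device are blind to any offset or slope error. The residual SD of device on DXA is blind to an offset.

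The invariance needs no assumption. The size does: reversal is nearly certain (96% to 97.5%) for a 3 to 5 point offset with scatter SD 2.5 against 3.0, and ranges from 0.6% to 92% for a slope of 0.7 as the DXA SD goes from 6 to 10. Nothing in the document shows that VBC or any comparator is miscalibrated, so it cannot be said that the study's ranking would be wrong. What can be said is that the stated test could not tell. The change should be made, but the planned Bland-Altman plots keep this from being a fatal flaw.

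**What to change.** In Statistical Design and Analysis:

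- Base the accuracy conclusion on raw error, device %fat minus DXA %fat. For each device report the mean difference, the limits of agreement, and either RMSE or mean absolute error, with 95% CIs.
- Compare VBC with each other device by the paired within-participant difference in absolute or squared error, with a CI. Choose the one that matches the summary above, before the data are analysed.
- Keep regression for the association aim and as a description of calibration. State the response variable, and report the intercept against 0 and the slope against 1 with CIs.
- Do the same in the BodPod-reference series.

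The cost is a change of wording and a little more analysis on measurements already planned, with no further participants or visits. The downside for the sponsor is that VBC's headline figure may look less favourable than an R2.

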#### **Measurements:**

All subjects will have body circumferences, DXA, Bod Pod, BIA, and VBC measurements. Note that times listed below include the subject moving from one lab to another.

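### The hypothesis says VBC is at least as accurate as DXA, but its named test uses DXA as the reference and can show only agreement with DXA

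*Combined protocol and SAP*

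**What the plan says.** The Hypothesis section states that the "VBC device will be equal to or more accurate than clinical grade (DXA, Bod Pod) and BIA systems" for measuring body composition. DXA is thus one of the methods that VBC is expected to match or beat.

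The Statistical Design and Analysis section says that regression will "test the main study hypothesis with %fat measured by the VBC device and by DXA as the reference method". Other test systems, with BIA as the example, get similar comparisons. The section adds "A secondary series of analyses will be conducted using BodPod as the reference method" and "Bland-Altman plots will be used to detect between-method bias". Coefficients of variation come from duplicate measurements.

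The Aims section begins "The study hypothesis will be tested as follows" and then lists two aims: "Identify the associations of body composition acquired by the VBC with those estimated by DXA, BodPod, and BIA" and "Describe the precision and accuracy of the VBC-derived scans". Neither sets VBC's error beside DXA's.

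**The concern.** A difference between VBC and DXA contains the errors of both methods. When DXA is the reference, the whole difference is charged to VBC, and DXA's difference from itself is zero. The analysis therefore yields no error figure for DXA with which VBC's could be compared.

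Because the plan calls this regression the test of the main hypothesis, a close fit to DXA would count, on the plan's own terms, as support for accuracy equal to or better than DXA's. This is the study's only stated hypothesis, and for its DXA clause that conclusion would not follow from the analysis.

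**Working it through.** The plan gives no error SDs and no figure to reproduce for this point. All SDs and correlations below are assumptions, in %fat points. The only design input is n=132.

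**1. What the VBC-DXA pair can identify.** Let T be true %fat, DXA = T + e_D and VBC = a + bT + e_V, with independent normal errors. The intercept a is set so that the mean VBC-DXA difference is zero in both models. Then:

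- var(DXA) = var(T) + var(e_D)
- var(VBC) = b² var(T) + var(e_V)
- cov = b var(T)

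| | Model A | Model B |
|---|---|---|
| SD of T | 8 | √67 = 8.19 |
| VBC slope b | 1 | 64/67 = 0.955 |
| DXA error SD | 2 | 1 |
| VBC error SD | 1 | √(65 − 64²/67) = √3.866 = 1.97 |
| var(VBC) | 64 + 1 = 65 | 65 |
| var(DXA) | 64 + 4 = 68 | 67 + 1 = 68 |
| covariance | 64 | 0.955 × 67 = 64 |
| RMSE of VBC against truth | 1.0 | √((1 − 0.955)² × 67 + 3.866) = √(0.134 + 3.866) = 2.0 |
| RMSE of DXA against truth | 2.0 | 1.0 |

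The means, variances and covariance are the same, so every planned VBC-DXA result is the same:

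- Slope of VBC on DXA: 64/68 = 0.941.
- R-squared: 64²/(65 × 68) = 0.927.
- SD of the differences: √(65 + 68 − 128) = √5 = 2.24, so limits of agreement of ±1.96 × 2.24 = ±4.4.
- Bland-Altman trend: cov(VBC − DXA, their mean) = (65 − 68)/2 = −1.5.

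The accuracy ranking nevertheless reverses, and a larger sample does not help. The same reversal occurs if Model A's true SD is 6 (Model B slope 36/39 = 0.923) or 10 (100/103 = 0.971). Coefficients of variation from duplicate VBC scans describe repeatability and leave any stable subject-level error unseen.

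**2. What Bod Pod adds.** The Measurements section says "All subjects will have body circumferences, DXA, Bod Pod, BIA, and VBC measurements", so a third method is available. I added a Bod Pod error independent of the others and compared mean |VBC − BodPod| with mean |DXA − BodPod| in 20,000 simulated trials of 132. The correct method came out closer in about 95% (Bod Pod error SD 4), 98% (SD 3) and 99.9% (SD 2) of trials, under Model A and Model B alike.

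That result depends on independence. With all error SDs truly 2, a correlation of 0.1 between DXA's and Bod Pod's errors lets VBC come out closer in only 26% to 27% of trials instead of 50%; at 0.3 it is 2%. The same correlations between VBC's and Bod Pod's errors give 73% to 74% and 98%. The planned data cannot estimate these correlations.

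**3. Precision of a paired comparison against DXA.** With all error SDs 2 and independent, the 95% CI half-width for mean |VBC − DXA| minus mean |other − DXA| is about 0.36 points at n=132. At n=66 it is about 0.36 × √2 = 0.51.

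**4. Why the reading must be fixed.** Subjects and Design plans two VBC scans and two BIA measurements, but one Bod Pod and one DXA. Suppose all single-reading error SDs are 2 and half of VBC's error variance is random between scans. The average of two VBC scans then beats a single Bod Pod reading in about 80% of simulated trials, although the two are equally accurate reading for reading.

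**The case against.** The strongest reply is that the plan holds more than the VBC-DXA pair. Step 2 shows that Bod Pod data on every subject could separate the two models well if errors are independent. That stands, and it limits the point to the named main analysis. It does not remove it: the BodPod-reference series is secondary, DXA is not named there as a test method, and no comparison of the two errors is planned.

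A second reply is that the overreach sits in one sentence. The Objectives promise a comparison and the Aims promise association and description. That also stands, but the Aims are introduced as the way the hypothesis is tested, and the analysis section repeats the link. Reading equality with DXA as agreement is reasonable, and is what the fix writes down.

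Three stronger inferences are not supported:

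- *That the whole hypothesis is untestable.* VBC, BIA and Bod Pod can each be judged by closeness to DXA, provided they share no error with DXA, or the same amount.
- *That the single DXA scan causes the problem.* A second scan would show DXA's repeatability, not its systematic error in a subject.
- *That Bod Pod in particular shares error with DXA.* The protocol describes no shared error for any device, so this is a general assumption to state for all of them.

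**Conclusion.** The point holds for the DXA clause of the hypothesis and should be fixed. Regression and Bland-Altman analysis against DXA can support a statement about agreement with DXA. They cannot support accuracy equal to or better than DXA's, at any sample size, without outside assumptions about the errors. That conclusion comes from the structure of the comparison; the SDs in the two models only illustrate it. A reader should not infer that the trial can say nothing about VBC against DXA: a BodPod-reference comparison could, conditional on independent errors, but it is not specified. Data collection is unaffected. What changes is what the main analysis may conclude.

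**What to change.** 1. **Hypothesis section.** Remove the claim that VBC is at least as accurate as DXA. Suggested text:

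   > VBC %fat will be assessed for agreement with DXA (mean bias and 95% limits of agreement). Its absolute difference from DXA will be compared with that of BIA and of Bod Pod.

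2. **Statistical Design and Analysis section.** Add paired comparisons of |VBC − DXA| with |BIA − DXA| and with |BodPod − DXA|, each as a mean paired difference with a 95% CI.
   - Use one reading per method, for example the first VBC and the first BIA reading.
   - Analyse each BIA system in the subjects measured on it. The BIA section gives InBody and SECA as alternatives for the professional system, so n may be below 132 for each. An even split (an assumption) gives 66.
   - State the assumption that the compared methods share no error with DXA, or the same amount.

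3. **Only if a VBC-versus-DXA accuracy statement is kept.** Make it exploratory within the BodPod-reference series. Name DXA as a test method there, compare |VBC − BodPod| with |DXA − BodPod| in pairs on single readings, and show the result over a range of assumed error correlations of each method with Bod Pod.

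The cost is wording in two sections and a few paired analyses of measurements already planned. The downside is that accuracy relative to DXA is no longer a main conclusion.
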